9.3.4 Tumor Response

For this study, response will focus on the injected tumor(s) and be based on criteria according to those in RECIST v1.1.[6] In addition, overall tumor response will be assessed according to RECIST 1.1 criteria.

The following criteria will be used to define response in injected tumor(s):

- Complete Response (CR): Disappearance of the injected tumor(s).
- Partial Response (PR): At least a 30% decrease in the longest diameter (LD) of the injected tumor(s), taking as reference the smallest LD.
- Progression (PD): At least a 20% increase in the LD of the injected lesion(s), taking as reference the smallest LD recorded on study (this includes the baseline LD if that is the smallest on study). Note: appearance of one or more new lesions will be considered progression in assessing overall tumor response.
- Stable disease (SD): Neither sufficient shrinkage to qualify for PR nor sufficient increase to qualify for PD taking as reference the smallest LD while on study.

Target tumors accessible for needle injection on physical examination will be injected. Size of the injected tumor masses will be measured with ruler or calipers, as possible, and it is preferable if the same practitioner measures using the same technique at each visit.

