9.3.5 Radiographic Imaging

Lesions will also be assessed qualitatively using MRI or CT scan with the site's available MRI and CT techniques. The same imaging technique will be used for all evaluations. The target lesions and injected tumors for intratumoral administration will be assessed radiographically at baseline and within 2 weeks of Ad/PNP-F-araAMP on the first, third, and last cycle (and during the second cycle for those showing PD). In subjects who have CR, PR or SD on imaging 2 weeks after the last drug administration, follow-up imaging will be obtained again approximately 6 weeks later. Non-neck tumor sites may be followed by conventional CT/MRI.

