Tumor response in the injected tumor(s) will be assessed by physical examination (tumor measurement using ruler or calipers, if tumor can be assessed by palpation) as well as by radiographic imaging (magnetic resonance imaging [MRI] or computed tomography [CT] scan). The same methods to assess the injected tumor(s) will be used at baseline and subsequent time points.

Participants will be assessed for safety frequently, including Day 14 of each cycle. Participants will be assessed 4 weeks after completion of the last or fifth cycle. During the study, participants will be monitored for AEs including signs of infection, and changes in hematological or chemistry parameters (see Appendix 2, Protocol Study Procedures Table).

Participants who withdraw early from treatment will be asked to complete Day 56 (of the last treatment cycle) study visit evaluations. The study schema is presented in Figure 1.

Figure 1: Study Design

DLT = Dose-limiting toxicity; IV = intravenously; PD = progressive disease, VP = viral particle;

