### 6.2.2 Secondary Efficacy Endpoints and Analyses

Secondary efficacy endpoints involving response, including progression, will be assessed 2 distinct ways:

- For injected tumors (per the criteria specified in protocol section 9.3.4), and
- Overall as determined per RECIST v1.1 (<http://www.ctep.info.nih.gov>).

Efficacy responses assessments for injected tumors should be performed using the (RECIST-like) assessment according to the criteria established in section 9.3.4 (Tumor Response) of the protocol (CR, PR, PD, SD). Per the protocol, this response for injected tumors is the primary focus for response, with the efficacy endpoint of primary focus being ORR for injected tumors.

Overall efficacy response assessments should be performed per RECIST 1.1 for target and non-target tumors without consideration for which tumors were treated with the study agent. Per the protocol, this overall response per RECIST 1.1 is not the primary focus for response. Total tumor burden is also being evaluated because there is a possibility of immune-mediated anti-tumor benefit.

RECIST and protocol established response evaluation criteria should be performed/evaluated in combination with CT scan/MRI at the timepoints specified in the protocol (Visit 7 of the first,

second (if PD after first cycle), third, and last cycle. Participants with CR, PR, or SD in the injected tumor at Day 14 of the fifth or last cycle will have imaging on Day 56).

To emphasize:

- Injected tumors will not be assessed per RECIST v1.1 but solely per the criteria (from protocol section 9.3.4) which are specified below.
- Many of the endpoints differ for injected tumors vs. overall as determined per RECIST v.1.1 due to differences in their underlying component definitions of CR, PR, and PD.
- All efficacy endpoints are secondary.

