### **Injected Tumor Response Criteria Details**

The following criteria will be used to define response in injected tumors:

- Complete Response (CR): Disappearance of the injected tumor(s).
- Partial Response (PR): At least a 30% decrease in the longest diameter (LD) of the injected tumor(s), taking as reference the smallest LD.
- Progression (PD): At least a 20% increase in the LD of the injected lesion(s), taking as reference the smallest LD recorded on study (this includes the baseline LD if that is the smallest on study). Note: appearance of one or more new lesions will be considered progression in assessing overall tumor response.
- Stable disease (SD): Neither sufficient shrinkage to qualify for PR nor sufficient increase to qualify for PD taking as reference the smallest LD while on study.

Regarding injected tumors, only tumors identified as target per RECIST 1.1 at the initial study visit should be treated with the study agent (AdPNP). It is possible, based on the size(s) and location(s) of the target tumor(s), that not all target tumors will be treated with the study agent. At each administration, investigators should treat only the same tumor(s) based on those target tumors treated at the initial treatment visit. No other target tumors should be treated with the study agent at any subsequent visit. Non-target tumors should not be treated with the study agent. Response for injected lesions is assessed by the investigator and recorded in the eCRF.

Regarding non-injected tumors, the protocol does not define response assessment criteria for these tumors. Therefore, efficacy response for non-injected tumors will be taken into consideration only as an input to the RECIST 1.1 response assessment. No formal criteria-based response assessment will be performed or analyzed for non-target tumors alone. Any observable effect on non-injected tumors may be recorded by investigators in the study database.

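### Injected-tumor progression is a bare 20% rise over the smallest diameter with no minimum in millimetres, so reading error in a small or shrunken tumor can be called progression

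*SAP*

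**What the plan says.** **The rule.** SAP 6.2.2 (Injected Tumor Response Criteria Details) defines PD as "At least a 20% increase in the LD of the injected lesion(s), taking as reference the smallest LD recorded on study". Protocol 9.3.4 has the same rule, "taking as reference the smallest LD recorded on study (this includes the baseline LD if that is the smallest on study"). Neither text sets a minimum change in millimetres or asks for PD to be confirmed.

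**No other rule fills the gap.** SAP 6.2.2 states: "Injected tumors will not be assessed per RECIST v1.1 but solely per the criteria (from protocol section 9.3.4) which are specified below".

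**Measuring method.** SAP 3.1, like Protocol 2.5, has injected tumors assessed "by physical examination (tumor measurement using ruler or calipers, if tumor can be assessed by palpation) as well as by radiographic imaging", and adds: "The same methods to assess the injected tumor(s) will be used at baseline and subsequent time points". Protocol 9.3.5 says: "The same imaging technique will be used for all evaluations". SAP 6.2.2 ties response evaluation to CT/MRI at set visits: Day 14 of the first, third and last cycles (and of the second after early PD), and Day 56 of the last cycle for participants without PD. Calipers are read more often, and having the same reader each time is a preference only (Protocol 9.3.4). Protocol 9.3.5 calls the imaging assessment qualitative. No passage says which method supplies the longest diameter (LD) for the PD rule.

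**What PD does.** The earliest PD finding is the PFS event (SAP 6.2.2.2). PD closes the windows for best overall response (6.2.2.1) and time to response (6.2.2.3), ends duration of response (6.2.2.5) and enters the 28-day durability calculation (6.2.2.1). Responses need no confirmation (6.2.2.1).

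**The concern.** A purely relative rule needs only a tiny absolute change when the reference is small, and the reference is smallest in responders. A tumor that goes from 20 to 12 mm and then reads 15 mm has PD (15/12 = 1.25) while still 25% below baseline (15/20 = 0.75). After complete response the reference is 0 mm and a percentage rise cannot be computed, yet Protocol 4.2 expects some tumors to recur after complete response.

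Injected-tumor response is the primary focus of the efficacy assessment (SAP 6.2.2). Short duration of response in Phase 1 is the protocol's stated reason for testing repeat dosing (Protocol 2.3). Injected-tumor PFS and duration of response would be biased short if reading error were counted as progression.

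**Working it through.** **Plan's own figures.** The documents give no figure for misclassified PD. The one related figure is the ORR design (SAP 3.3): at least 3 responses in 10, exact binomial. P(X ≥ 3 | 10, 0.40) = 0.833 and P(X ≥ 3 | 10, 0.10) = 0.070, so the stated 83% and 7% reproduce.

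**Millimetres needed for PD** (0.2 × smallest LD): 1 mm at 5 mm, 2 mm at 10 mm, 3 mm at 15 mm, 4 mm at 20 mm, 6 mm at 30 mm. A 5 mm minimum therefore matters only below 5/0.2 = 25 mm. A 25 mm sphere has volume (π/6) × 2.5³ = 8.2 ml. This roughly covers the three smallest rows of the injection-volume table in Protocol 4.2, so the plan expects such lesions.

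**Two readings of an unchanged lesion.** With true diameter L and independent normal errors of SD s, P(second ≥ 1.2 × first) = 1 − Φ(0.2L / (s√2.44)), because 1 + 1.2² = 2.44. For L = 15 mm:
- s = 0.5: 3/0.781 = 3.84, about 0.01%
- s = 1.0: 3/1.562 = 1.92, 2.7%
- s = 1.5: 3/2.343 = 1.28, 10%

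**Whole imaging schedule.** This was simulated with a baseline scan and four later scans (about Days 14, 70, 126 and 168), each compared with the smallest earlier reading. Assumptions, none of them from the documents: one lesion, independent normal error constant in mm, and readings rounded to whole mm. The table gives the chance of at least one false PD.

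| Lesion | No minimum, SD 0.5 / 1.0 / 1.5 mm | 5 mm minimum, SD 1.0 / 1.5 mm |
|---|---|---|
| Stable 15 mm | 0.4% / 26% / 56% | 1% / 13% |
| Stable 20 mm | 0% / 6% / 31% | 1% / 13% |
| Falls from 20 to 12 mm by the first scan, then stays | 0.5% / 24% / 51% | 0.5% / 8.5% |
| Stable 30 mm | 0% / 0.1% / 4% | no change |

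Without rounding, the stable 15 mm lesion gives 18% and 50% at SD 1.0 and 1.5 mm.

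**Which endpoints move.**
- *PFS and duration of response (injected tumors):* any false PD ends them.
- *ORR:* a recorded CR or PR stays, because confirmation is not required. A response is lost only if false PD comes before it. If that cost 10%, 20% or 30% of responders (assumed), P(X ≥ 3 | 10, 0.40 × (1 − f)) would be 76%, 67% or 56%.
- *Durable response:* lost if false PD precedes the first response, or falls too soon after it. Nominal gaps between the four scans are 56, 56 and 42 days, so the next scan usually falls beyond 28 days. The gap shrinks to 28 days only when the last cycle directly follows cycle 1 or cycle 3. Visit windows can then bring the PD date inside the limit.
- *OS and the overall RECIST 1.1 endpoints:* do not use this rule.

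**The case against.** **Measuring method.** A reader might infer that the plan lets any method be compared with any other. It does not: methods stay the same over time, one imaging technique is used throughout, and response is evaluated with CT/MRI. What remains is narrower. Two methods run in parallel, and the text does not say which supplies the smallest LD and the later LD.

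**Pooled smallest diameter.** The words on the smallest LD recorded could be read as the minimum of all caliper and imaging readings, which would give much higher error rates. No passage directs that, so no such figure is used here.

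**Effect on response.** A reader might infer that false PD ends every response endpoint. A recorded response still counts in ORR, and a later PD does not displace a valid stable disease as best response.

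**Size.** The reading SD is assumed, and at 0.5 mm the effect nearly vanishes at 15 mm and above. Several injected tumors would dilute it: if two 15 mm LDs were summed (an assumption), 26% to 56% would fall to 3% to 24%. This objection stands, so the result is a range and not an estimate.

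**Nature of the rule.** Any rule based on the smallest value can call PD below baseline. With a 5 mm minimum, 12 to 17 mm is still PD at 15% below baseline (17/20 = 0.85). The absolute minimum addresses reading error only. Also, 5 mm has no source in these documents.

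**Conclusion.** The concern holds as a cheap improvement. The rule has no absolute minimum, RECIST 1.1 is expressly excluded for injected tumors, and a single unconfirmed PD finding is decisive. At a small reference diameter, reading error *can* be called progression; the documents do not show that it generally will be.

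For lesions of 15 to 20 mm and an assumed SD of 1.0 to 1.5 mm, the chance over four scans runs from 6% to 56%. It is 24% to 51% for the responder who falls to 12 mm. At SD 0.5 mm it is 0.5% or less in the cases tabulated, and at 30 mm a 5 mm minimum changes nothing. The exposure is mainly to injected-tumor PFS and duration of response, and only conditionally to durable response and ORR. All are secondary endpoints. The unnamed method and the undefined percentage after complete response are gaps in the text whatever the reading error.

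**What to change.** For endpoint derivation only, in SAP 6.2.2:

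1. Define injected-tumor PD as an increase over the smallest LD of at least 20% **and** at least a prespecified absolute amount, for example 5 mm. The sponsor should justify the value.
2. Take both the smallest LD and the comparison LD from the response-assessment visits and from one prespecified method, the CT/MRI reading.
3. State how reappearance after complete response is dated as a PD event.
4. Derive this status from the recorded LDs. The investigator assigns the eCRF response, so new SAP wording alone would not change those entries.

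The cost is SAP text, some programming, and a check that scan LDs are recorded in mm for each injected tumor, since Protocol 9.3.5 calls imaging qualitative. True regrowth of a very small lesion may be dated one scan later.

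Injected-tumor progression also governs stopping of treatment (Protocol 2.5 and 4.2), and Protocol 4.2 allows treatment to resume when a tumor recurs after complete response. The sponsor must reconcile those passages with the endpoint definition. No clinical rule is proposed here.

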10.2 Secondary Outcome Measure**Title:**

The secondary objective of the study is to evaluate the anti-tumor activity of repeat administration of Ad/PNP-F-araAMP.

Timeframe:

Secondary outcome will be evaluated on a longitudinal basis and at study completion.

Safety Issue:

N/A, please see above

10.3 Primary and Secondary Outcome Measures-Discussion:

Primary Outcome Measurements for this study are directed towards safety and will be evaluated by: medical history, physical examination, vital signs, inspection of tumor site, performance status,

EKG, chest X-ray (CXR), blood chemistry, hematology, CD4/CD8 T-cell counts, urinalysis, PT/PTT, blood sample for adenovirus, urine for adenovirus, F-Ade plasma level, blood sample for antibody against adenovirus, and monitoring adverse events. Additional detail regarding these endpoints is furnished in Section 9.1, 9.2, and 9.3.

Secondary Outcome Measurements are directed towards efficacy and will include: Objective response rate (ORR), defined as the percentage of patients with a best overall response (BOR) of a complete response (CR) or a partial response (PR). BOR is the best response achieved during the 5 cycles of treatment, for injected tumors and overall, as determined by RECIST v.1.1. Other measurements will include:

- Durable response rate defined as a BOR of CR or PR for injected tumors and overall, as determined by RECIST v. 1.1 persisting for at least 4 weeks.
- Time to response (TTR) defined as time from first intratumoral injection to date of first response value of CR or PR for injected tumors and overall, as determined by RECIST v.1.1.
- Overall survival (OS) defined as time from first intratumoral injection to date of progression or death for any cause, whichever occurs first.
- Progression free survival (PFS) defined as time from first intratumoral injection to date of progression or death for any cause, whichever occurs first.
- Duration of response (DOR) defined as time from first documentation of CR or PR for injected tumors and overall, as determined by RECIST v.1.1 until disease progression or death for any cause, whichever occurs first.

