10.3.3 Measurement Methods

Primary outcome measurement methods will include clinical evaluation (physical examination, medical history, performance status, vital signs, evaluation of tumor site for evidence of tissue injury) by investigators conducting the study (or their designees). Laboratory and additional parameters (EKG, CXR, blood chemistry, hematology, CD4/CD8 T-cell counts, urine analysis, PT/PTT, etc.) will be measured according to standard hospital/clinic procedures, and as detailed in Section 7 of this document.

Secondary outcome measurement methods are defined in Sections 9.3.4 and 9.3.5 and will be performed according to RECIST 1.1.

Special Studies include

Blood samples for adenovirus, urine for adenovirus, F-Ade plasma level, blood sample for antibody against adenovirus, tumor biopsy for studies of PNP activity, histochemistry, growth fraction, and adenoviral distribution. Specific studies are described in Section 8.

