### 3.2 Randomization and Blinding

PNP-002 is an unblinded, open label study.

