#### 6.2.2.1 Best Overall Response, Objective Response Rate and Durable Response Rate

##### **Best Overall Response**

Separately for injected tumors and overall (per RECIST v1.1), a participant's best overall response (BOR) is determined by the highest qualitative value assessed during the study for the following hierarchy of objective response results: CR > PR > SD > PD > NE. In order for a valid value of SD to be assigned, there must be evidence of stable disease for at least 6 weeks. If the minimum time for SD has not been met on the first assessment, the assignment of BOR will depend on subsequent response assessments. Participants which do not have follow up data after a first assessment of SD prior to the minimum time requirement will be considered as not evaluable (NE). BOR will be based on assessments collected after the first intratumoral injection until disease progression; assessments collected after the start of new anticancer treatment will not be considered. Confirmation of response will not be required for BOR. Participants who do not have any post-baseline results for response will be considered as not evaluable (NE).

Separately for injected tumors and overall (per RECIST v1.1), BOR will be summarized using the efficacy evaluable population.

Waterfall plots of BOR results for each criterion will be presented graphically using maximum percent reduction. Swimmer plots identifying participant response patterns over time will also be separately provided.

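### Injected-tumor ORR rests on open-label investigator entries; the protocol is inconsistent about the criteria behind them, and the SAP plans no check that entries followed the rule it adopts

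*SAP*

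**What the plan says.** SAP 6.2.2 describes response in injected tumors as the main interest, "with the efficacy endpoint of primary focus being ORR for injected tumors". It gives the source of that response as follows: "Response for injected lesions is assessed by the investigator and recorded in the eCRF". SAP 3.2 adds: "PNP-002 is an unblinded, open label study". Under SAP 6.2.2.1 a participant's BOR "is determined by the highest qualitative value assessed during the study", and a response does not have to be confirmed.

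On the criteria, SAP 6.2.2 is explicit: "Injected tumors will not be assessed per RECIST v1.1 but solely per the criteria (from protocol section 9.3.4) which are specified below". It also says that many endpoints differ between the two assessments because CR, PR and PD are defined differently. The protocol is less clear. Section 10.3 says "BOR is the best response achieved during the 5 cycles of treatment, for injected tumors and overall, as determined by RECIST v.1.1", and section 10.3.3 says "Secondary outcome measurement methods are defined in Sections 9.3.4 and 9.3.5 and will be performed according to RECIST 1.1".

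Tumor measurements enter the analysis in one place: "Waterfall plots of BOR results for each criterion will be presented graphically using maximum percent reduction". SAP 5.2 measures that reduction from baseline.

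SAP 3.3 and Protocol 12.1 treat 3 or more responses in 10 as enough to justify further study.

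**The concern.** An investigator reading the protocol alone could reasonably apply either rule to an injected tumor. The SAP, dated 19 October 2023 against a protocol of 6 May 2022, says which rule it intends. It cannot change calls already entered, and it has no step that would show whether they followed that rule. Since no confirmation is needed, a single favorable entry before progression makes a participant a responder. TTR, DOR and PFS for injected tumors are built on the same entries.

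The stake is the decision on further study. With 10 evaluable participants, one reclassified participant can move the result across the threshold. The waterfall plot and the BOR table could also appear to contradict each other for the same participant, and no reconciliation is planned.

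**Working it through.** **1. What each section says about injected tumors**

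| Place | Criterion |
|---|---|
| Protocol synopsis, Endpoints | RECIST 1.1 on one reading; the closing phrase may cover only overall response |
| Protocol 9.3.4 | Its own CR, PR, PD and SD definitions, modelled on RECIST 1.1 |
| Protocol 10.3 | RECIST 1.1 for both injected tumors and overall |
| Protocol 10.3.3 | Points to 9.3.4 and 9.3.5, but performed to RECIST 1.1; ambiguous |
| Protocol 10.3.5 | RECIST 1.1, with no exception for injected tumors |
| Protocol 12.6 | 9.3.4 for injected tumors, RECIST 1.1 for overall |
| SAP 6.2.2 | 9.3.4 only |

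**2. How much the PR reference matters**

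The documents do not reproduce the RECIST 1.1 definitions. That the two sets differ rests on the SAP's own statement. As an illustration I compare the two references that do appear in the documents: the smallest LD (Protocol 9.3.4 and SAP 6.2.2, for PR) and baseline (SAP 5.2, for the waterfall). Hypothetical LDs are 50 mm at baseline, then 40, 32 and 26 mm.

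| LD (mm) | Change from baseline | Change from smallest prior LD |
|---|---|---|
| 40 | 40/50 − 1 = −20% | 40/50 − 1 = −20% |
| 32 | 32/50 − 1 = −36% | 32/40 − 1 = −20% |
| 26 | 26/50 − 1 = −48% | 26/32 − 1 = −18.8% |

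Against baseline this is PR from the second assessment. Against the smallest prior LD it never reaches −30%, so it is never PR, yet the waterfall would show −48%. The smallest prior LD cannot exceed baseline, so the literal 9.3.4 wording gives the same number of PRs as a baseline reference or fewer.

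**3. The plan's own figures**

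Inputs from SAP 3.3: n = 10, null ORR 10%, alternative 40%, reject at 3 or more. With X ~ Binomial(10, p):

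P(X ≥ 3) = 1 − (1−p)^10 − 10p(1−p)^9 − 45p²(1−p)^8

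- p = 0.10: 1 − 0.3487 − 0.3874 − 0.1937 = 0.0702 (stated 7%).
- p = 0.40: 1 − 0.0060 − 0.0403 − 0.1209 = 0.8327 (stated 83%).

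Both reproduce. A result of 3/10 (95% Clopper-Pearson 6.7% to 65.2%) rejects the null; 2/10 (2.5% to 55.6%) does not.

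**4. Sensitivity to misclassified entries (assumed rates)**

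Let a share f of true non-responders be entered as responders at a true ORR of 10%. The apparent rate is 0.10 + 0.90f.

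| f | Apparent rate | P(X ≥ 3) |
|---|---|---|
| 0 | 0.100 | 7.0% |
| 2% | 0.118 | 10.4% |
| 5% | 0.145 | 16.7% |
| 10% | 0.190 | 29.2% |

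At f = 2% the 10% target is already passed. In the other direction, let a share m of true responders be entered as non-responders at a true ORR of 40%. The apparent rate is 0.40(1 − m). For m = 10% this is 0.36 and power falls to 75.9%. For m = 25% it is 0.30, with power 61.7%.

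**The case against.** The protocol writes out only one operational set of injected-tumor criteria, in 9.3.4. Its statistical section, 12.6, assigns that set to injected tumors, and the SAP confirms it. On this view sections 10.3 and 10.3.5 are loose wording, not a rival definition. That is largely right: the rule for analysis is settled. What stands is that sites also had the looser sections, and nothing planned tests which was followed.

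A reader might infer that the eCRF field already mixes calls made under two rules. The documents do not support that. The SAP also rests on a Protocol Clarification Letter (8 March 2023) and a CRF (2 November 2022), neither of which is available here, and the letter may have told sites which criteria to use. SAP 6.2.2 also describes separate RECIST 1.1 entries for overall, target and non-target lesions, which makes confusion less likely.

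A reader might also take investigator assessment itself as the fault. It is ordinary in a single-arm phase 1/2 safety study, and every efficacy endpoint here is secondary. SAP 3.3 disclaims formal efficacy hypotheses, and SAP 6.2.2.1 plans only an estimate with an interval. The 3-response rule is nonetheless stated as the basis for further study.

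The SAP does plan efficacy listings by participant, waterfall plots and swimmer plots, and table shells are kept separately. These may expose some discrepancies. However, a waterfall bar that disagrees with the tabulated BOR would not show a miscall, because the plot is referenced to baseline and PR to the smallest LD.

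Finally, the same open-label sites supply the caliper measurements, so deriving the category from diameters cannot cure biased measurement. That objection stands in full.

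**Conclusion.** The concern holds as a gap in checking. The main efficacy result depends on unconfirmed, open-label entries. The protocol is inconsistent about the criteria behind them, and the SAP adopts one rule without verifying that entries obeyed it. The 9.3.4 rule is also incomplete: it does not say how several LDs are combined or whether the caliper or the imaging diameter prevails, and Protocol 9.3.5 describes imaging assessment as qualitative.

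A single call can decide the 3-of-10 rule. The figures of 10.4%, 16.7% and 29.2% are conditional on assumed error rates of 2%, 5% and 10%. They show how fragile the threshold is; they do not estimate this trial's type I error. They also assume 10 evaluable participants, independent calls, and that the threshold applies to injected-tumor ORR, which SAP 3.3 does not say but SAP 6.2.2 implies.

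**What to change.** 1. Reconcile the protocol synopsis and sections 10.3, 10.3.3 and 10.3.5 with section 9.3.4. In both documents, state the PR reference (baseline or smallest LD), how several injected lesions are combined, and whether the caliper or imaging diameter is used. This must come first. Programming the present wording would fix the literal smallest-LD reference, under which the 48% shrinkage in the example is never PR.

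2. Add a sensitivity analysis to SAP 6.2.2. Derive injected-tumor CR, PR, SD and PD at each assessment from the recorded diameters under the completed rule. If calls were entered before the rule was settled, also derive them under the other PR reference. Report ORR and the result against the 3-response threshold for the derived and the investigator-entered responses. List every participant whose classifications differ, with the diameters.

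The cost is a wording amendment, some programming, one table and one listing. No extra scan or reader is needed. A derived category cannot reflect a clinical reason for an investigator's call, so both results should be shown. The report should say that the analysis tests consistent application of the rule, not the accuracy of open-label measurements.
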